Title: Anterior Openbite (AOB) Malocclusions in Adults: Recommendations, Treatment, and Stability.

Précis: Almost all research on AOB treatment and stability is from retrospective case series. Therefore, this study has tremendous potential to provide practitioners with stronger evidence about AOB treatment outcomes and stability for adults. It will also provide information about retention outcomes. Additionally, the gathering of patient-reported data about the decision to pursue a specific treatment option and patient satisfaction after treatment may be extremely valuable.

This is a prospective, observational 3.5 year cohort study of approximately 840 adult patients in active orthodontic treatment for AOB who **expect** to have treatment completed within 24 months of enrollment into the study from approximately 210 National Dental Practice-Based Research Network (National Dental PBRN) orthodontists or dentists who routinely perform orthodontic treatment.

Objectives: **Primary:** The primary objective is to estimate the proportion of patients 1) treated successfully (determined at end of active treatment), and 2) whose treatment is stable (determined at one year post active treatment).

The primary outcome measure to determine success of treatment will be overbite at the end of treatment, and the primary measure to determine stability of treatment ascertained one year after removal of orthodontic appliances is the overbite measurement.

Secondary: The secondary objectives are to:

1. Identify how dentofacial characteristics, as well as patient and practitioner characteristics, influence:
 - a. Treatment recommendations, and
 - b. Acceptance of treatment recommendations.
2. Identify how treatment modalities, as well as dentofacial, patient, and practitioner characteristics, are associated with the following, both determined at the time orthodontic appliances are removed (end of active treatment):
 - a. Treatment success, and
 - b. Patient satisfaction.

3. Identify how retainer regimens, as well as treatment modalities, dentofacial, patient and practitioner characteristics are associated with the following, both determined one year after end of active treatment:
 - a. Treatment stability, and
 - b. Patient satisfaction.

Population: The study will include approximately 840 adult National Dental PBRN practice AOB patients age 18 or older that are currently in active treatment, and **expect** to have treatment completed within 24 months of enrollment into the study.

Number of Sites: Approximately 210 National Dental PBRN practitioners.

Study Duration: Approximately 3.5 years

Subject Participation Duration: Approximately 3 years

Estimated Time to Complete Enrollment: Approximately 11 months

Schematic of Study Design:

Practitioner Screening/Enrollment

- Recruit, enroll, and train practitioners. Practitioner completes Practitioner Characteristics Form.

Patient Enrollment/Baseline, Active
Treatment Stage (Stage 1 [S1])

- At a routine orthodontic visit:
- Verify eligibility.
 - Obtain informed consent and assign subject ID.
 - Patient and Practitioner complete Enrollment Visit data collection forms.
 - Submit initial cephalometric x-ray and intra-oral frontal photograph.

Appliance Removal,
End of Active AOB Treatment
(Stage 2 [S2], Visit 1 [V1]; complete
within ~24 months after S1)

- At the time of appliance removal:
- Measure the height of the right maxillary central incisor.
 - Patient and Practitioner complete End of Active Treatment data collection forms.
 - Obtain intra-oral frontal photographs, one taken in maximum intercuspation, and another one with the incisors slightly apart.
 - Submit end of active treatment cephalometric x-ray and intra-oral frontal photographs.

Retainer Check Visits
(Stage 2, Visits 2-x; varies based
upon retention visit intervals)

- At the time of **each** routinely scheduled retainer check appointment:
- Patient and Practitioner complete Retainer Use data collection forms.

Final Study Visit (Stage 3 [S3])
(S2, V1 + 10 to 24 months)

- Approximately 1-year Post Appliance Removal:
- Measure the height of the right maxillary central incisor.
 - Patient and Practitioner complete Final Study Visit data collection forms.
 - Obtain intra-oral frontal photographs, one taken in maximum intercuspation, and another one with the incisors slightly apart.
 - Submit intra-oral frontal photographs.

2 INTRODUCTION: BACKGROUND INFORMATION AND SCIENTIFIC RATIONALE

2.1 Background Information

Anterior openbite (AOB) may be defined as a condition in which the maxillary and mandibular incisors do not touch when patients bite (in their normal position) on their back teeth. Typically, when individuals bite on their back teeth, their incisors will touch lightly, and thus AOB is considered to be an abnormal bite relationship, or malocclusion. Severe AOB may also affect speech and function (Appendix B, Figure 1). Sometimes, patients may also be concerned about the appearance of their incisors.

Data from National Health and Nutrition Examination Survey (NHANES) III indicate that the prevalence of AOB in the US population is about 3.5% across all age ranges¹. AOB is classified into two types: dental in origin, and skeletal in origin². Dental AOBs are characterized by relatively normal vertical facial proportions, and the etiology of the AOB is primarily due to the intruded position of the incisors (Appendix B, Figure 2). This intrusion often may be caused by habits, such as sucking a thumb or finger. In children, dental AOBs may spontaneously resolve if the habit is discontinued in early mixed dentition. Skeletal AOBs are characterized by steep mandibular plane angles, as well as decreased posterior facial height and increased anterior facial height (Appendix B, Figure 3). The geometry of the mandible and maxilla in these patients can require significant extrusion of the incisors (as well as the canines and premolars) to achieve positive overlap of the teeth. Orthodontists generally agree that skeletal AOBs are more challenging to treat and retain, as the etiology is often due to inherent growth patterns, which are difficult to control. Also, as mentioned earlier, a large degree of extrusion may be necessary to compensate for the increased anterior facial vertical dimension, unless orthognathic surgery is considered.

The current evidence on AOB treatment and stability is based largely on retrospective case series. There are reports that surgery may be more stable than orthodontic therapy^{3, 5}, and that extraction therapy may be more stable than non-extraction therapy⁷ (Appendix B, Figures 4 and 5). It is difficult to directly compare conventional to surgical treatment because studies measuring conventional orthodontic treatment typically report on adolescent patients, while the surgical literature reports primarily on adults. The success and stability for more recent techniques like temporary anchorage devices (TADs) and clear aligners have not been well investigated, with most of the literature consisting of case reports or case series⁸⁻¹⁵.

Based on case reports¹²⁻¹⁵, some orthodontists are using the clear aligner technique to treat AOBs. Many patients also favor aligners over conventional braces for esthetics and comfort. These are considerable advantages, and the case reports demonstrate that clear aligners can assist with bite closure. However, this technique does have limitations, including incomplete correction of tooth positions and difficulties in detailing the occlusion. Additionally, there are no published data about post-treatment stability

after treatment with clear aligners. Several case reports demonstrate that skeletal AOBs can be closed, but little information exists on the stability of the correction⁸⁻¹¹.

Conventional orthodontics is commonly recommended for AOB patients. It relies almost exclusively on dentoalveolar effects, mainly incisor extrusion, which may have a high potential for relapse. Because of this, additional strategies, such as Temporary Anchorage Devices (TADs) or surgery may be recommended. TADs are normally used in patients with skeletal AOB who might also be candidates for orthognathic surgery. TADs are used to assist with intrusion of molars, thereby allowing a closing rotation of the mandible, resulting in a deepening of the bite. TADs are invasive, but much less invasive than orthognathic surgery. They are also considerably less costly. Some researchers have reported that after treatment, molars may re-erupt, resulting in relapse of the AOB. If the treatment results and stability achieved with TADs are similar to that achieved with orthognathic surgery, then TADs would be preferable, due to their lower morbidity and cost. However, based upon the current literature, it is not known which treatment is better or more stable.

Of course, the most important outcome for AOB patients may be long-term stability, as closure of AOBs is often challenging to maintain (Appendix B, Figures 8-10)^{3,5}. The literature does point to some factors that may play a role in stability. For example, some clinicians feel that extraction therapy is helpful, as the incisors are tipped backward during space closure, and as they tip back, they also tip downward⁷. This can lead to better stability compared to a situation in which a crowded arch is expanded, tending to cause forward tipping and a more shallow overbite relationship. Other studies suggest that the cessation or altering of oral habits could improve stability, as these could be etiologic factors. For example, there are some reports that crib therapy to stop digit or tongue habits can be relatively stable¹⁶. As mentioned earlier, there are several systematic reviews addressing stability of conventional orthodontics and orthognathic surgery, but they are based on low quality studies³⁻⁶. Currently, there are few studies reporting long-term stability of TAD or clear aligner treatment⁹⁻¹¹. Additionally, only a few case reports describe the effectiveness of different types of retainers after treatment for AOB stability¹⁷⁻¹⁹.

Anterior openbite can be both a functional and cosmetic issue, and correcting it reliably, as well as retaining the correction, has proven to be challenging. Thus, conducting a well-designed study that addresses both treatment and stability may have high impact on the oral health of the public. This study may have significant benefits to future adult AOB patients. It may provide insight into the most effective and stable methods to treat and retain AOBs.

2.2 Rationale

The proposed study, which will take place in orthodontic and dental offices across the country that are part of the National Dental PBRN, is well-suited for a network study, as it will enable the assessment of practice trends for AOB from the entire country. At present, there are many strategies that are used to address AOBs. The

recommendations for treating a particular patient may depend on factors like the patient's age, the severity and nature of the AOB (dental vs skeletal), presence of habits, associated crowding, and each patient's goals and expectations. The treatment that a patient accepts can be influenced by all the factors above, as well as cost of the proposed treatments and a patient's willingness to consider surgical options like TADs or orthognathic surgery.

Further, since AOB occurs in less than 4% of the population, this National Network study will facilitate the collection of prospective data from a larger cohort of patients than could be obtained independently.

Almost all research on AOB treatment and stability is from retrospective case series. Therefore, this study has tremendous potential to provide practitioners with stronger evidence about AOB treatment outcomes and stability for adults. It will also provide information about retention outcomes. Additionally, the gathering of patient-reported data about the decision to pursue a specific treatment option and patient satisfaction after treatment may be extremely valuable.

2.3 Potential Risks and Benefits

There are no anticipated human subject safety risks to participating in this study. Research participants will not receive dental care as a study procedure, but will continue to receive normal clinical care as patients of the participating dentists and orthodontists. Risks of dental procedures provided as part of normal clinical care are not considered to be study-associated.

2.3.1 Potential Risks

Risks associated with routine orthodontic treatment, such as the risk of white spot lesions or root resorption, are not considered to be study-associated. As with any study, there is the possibility of breach of confidentiality. Appropriate precautions will be taken and procedures will be followed to maintain confidentiality. These include use of unique study codes for participants, encryption of electronic data for transmission to the coordinating center (CC), and password-protected computers for data storage. Compliance with all Institutional Review Board (IRB) regulations concerning data collection, data analysis, data storage, and data destruction will be strictly observed.

2.3.2 Potential Benefits

Participation in the study will provide no direct benefit to participants. This study may have significant benefits to future adult AOB patients, as it may provide insight into AOB treatment, stability and retention outcomes.

3 OBJECTIVES

3.1 Study Objectives

Primary: The primary objective is to estimate the proportion of patients 1) treated successfully (determined at end of active treatment), and 2) whose treatment is stable (determined at one year post active treatment).

Secondary: The secondary objectives are to:

1. Identify how dentofacial characteristics, as well as patient and practitioner characteristics, influence:
 - a. Treatment recommendations, and
 - b. Acceptance of treatment recommendations by the patient.
2. Identify how treatment modalities, as well as dentofacial, patient, and practitioner characteristics, are associated with the following, both determined at the time orthodontic appliances are removed (end of active treatment):
 - a. Treatment success, and
 - b. Patient satisfaction.
3. Identify how retainer regimens, as well as treatment modalities, dentofacial, patient and practitioner characteristics are associated with the following, both determined one year after end of active treatment:
 - a. Treatment stability, and
 - b. Patient satisfaction.

3.2 Study Outcome Measures

The primary outcome measure to determine success of treatment will be overbite at the end of treatment. Overbite will be measured in two ways. The first method is to record whether the incisors have positive overlap at the end of treatment, which indicates success. This will be judged from the frontal photographs at all three time points (baseline/enrollment, end of active treatment, and one year after end of active treatment). Second, using lateral cephalograms, the overbite will be measured relative to a standardized reference line (for example, occlusal plane), at two time points. At the first time point, we will see that relative to occlusal plane, the initial overbite is negative (no incisal overlap), and the distance between the maxillary and mandibular incisor tips can be measured in millimeters perpendicular to the occlusal plane. At the second time point, the final overbite should be positive (incisal overlap), and this overlap can be measured in millimeters perpendicular to the occlusal plane. Based on the measurements from the initial and final cephalograms, we will assess whether the overbite has been treated successfully (positive incisal overlap), as well as how much the overbite has improved (in millimeters).

The primary measure to determine stability of treatment ascertained one year after removal of orthodontic appliances is the overbite measurement. Since a cephalogram will not be taken one year after the end of treatment, this measurement will need to be assessed from the photographs. Overbite will be measured in two ways. The first is the dichotomous assessment of incisal overlap at the follow-up time; this will be performed in the same manner as stated in the preceding paragraph. A positive incisal overlap will be considered stable. The second method will be performed by utilizing the proportions of teeth in order to determine how much overbite change has occurred (see Appendix C). The orthodontist will be asked to measure the height of the right maxillary central incisor at the time of deband and at the final visit. Using this measurement, along with the end-of-treatment and follow-up photos, the overbite can be calculated at each time point, as well as the amount of overbite change.

Secondary outcome measures to examine how dentofacial, patient and practitioner characteristics influence a) treatment recommendations suggested by the orthodontists and b) acceptance of treatment recommendations by the patient include the following:

- Practitioner treatment recommendations include the practitioner's general strategies for openbite treatment (from practitioner characteristics form, e.g., whether and how often surgery is recommended), treatment recommendations (e.g. surgical option) presented to the patient, and patient's treatment goals (practitioner perspective);
- Patient acceptance of treatment recommendations includes the patient's self-report of the primary (ideal) treatment plan, whether or not the plan was accepted and why, and the patient's treatment goals;
- Dentofacial characteristics will be ascertained through examination and include: dental or skeletal nature of the openbite, millimetric measure of AOB, and amount of crowding;
- Patient characteristics include age, race, sex, insurance, and education; and
- Practitioner characteristics include the following: age, race, sex, years since received orthodontic training and orthodontic program.

Secondary outcome measures to examine how treatment modalities are associated with treatment success and patient satisfaction at the end of active treatment include the following:

- Treatment success is described above for the primary objective.
- Treatment modalities: Which teeth were extracted, if any; which if any of four treatment modalities were used (surgical component, fixed appliances, removable aligners, and/or TADs (mini-screws, mini-plates)).
- Patient satisfaction: The primary satisfaction measure will be overall satisfaction with treatment, (and secondarily, satisfaction with esthetics and function separately), ascertained by patient report at the end of active treatment.
- Other factors of interest for each include dentofacial characteristics (molar class, crowding, facial pattern, magnitude (millimeters) of overbite), practitioner characteristics (age, race, sex, years since received orthodontic training) and patient characteristics (age, race, sex, insurance, education, treatment

preference (whether patient agreed with primary recommendation), and patient treatment goal).

Secondary outcome measures to examine how retainer regimens, as well as treatment modalities, dentofacial, patient and practitioner characteristics are associated with treatment stability and patient satisfaction one year after the end of active treatment include the following:

- Treatment stability is described above for the primary objective.
- Retainer regimens include: Type (Hawley, Essix, bonded), whether full-time or part-time (nights only) and compliance with these recommended regimens (ascertained through practitioner and, separately, patient self-report).
- Patient satisfaction: Overall satisfaction with retainers (and secondarily, satisfaction with esthetics and function separately), all of which will be ascertained by patient report at one year after end of active treatment.
- Other factors of interest for each include success of treatment at end of active treatment, and as described above, dentofacial characteristics (molar class, crowding, facial pattern, magnitude (millimeters) of overbite), treatment modalities (extraction, then surgical component, fixed appliances, removable aligners, TADs), practitioner characteristics (age, race, sex, years since received orthodontic training) and patient characteristics (age, race, sex, insurance, education, treatment preference (whether agreed with primary recommendation), and treatment goal).

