Patients will complete an End of Active Treatment Form eliciting whether or not AOB was closed, if they were satisfied overall, satisfied with esthetics, satisfied with function, and if they would recommend the treatment they received to a friend if they had similar problem.

Routine visits within the year following end of active treatment. Practitioner will complete a Retainer Use Form based upon clinical history and examination, recording: 1) AOB status and any changes in alignment of upper or lower incisors; 3) assessment of patient's compliance; 4) any retainers and/or regimen changes; and 5) whether any additional adjunctive treatments have been completed since retention began.

Patients will complete a brief Retainer Use Form eliciting whether or not AOB is closed, how much they are wearing upper/lower retainers, and whether or not they are wearing retainers as requested.

Final visit, one year after end of active treatment. Practitioner will complete a Final Visit Form based upon clinical history and examination, recording the same information as on retainer use form and the current molar relationships.

Final intra-oral frontal photographs, one taken in maximum intercuspation, and another one taken with the incisors slightly apart, will be de-identified and uploaded for measurement of overbite. The practitioner will also measure the height of the right maxillary central incisor using the provided metal ruler.

Patients will complete a brief Final Visit Form eliciting whether or not AOB is (still) closed, current usage, if satisfied with retainer experience, satisfied with esthetics, satisfied with function, if they would recommend the treatment received to a friend if they had similar problem, and if satisfied with type of retainers received after treatment.

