11.2 Sample Size Considerations

Previous studies have reported success rates around 80% for treatment of AOB, and among those successfully treated, from 65% to 100% have been reported to be stable. These success and stability rates are likely overestimated due to reporting bias. We want to estimate both success and stabilization rates with 10% precision. Power is weakest when success and stabilization rates are lower (need larger sample size [patients], see table below).

Total number of patients needed to estimate proportions with 10% precision	
%succeed/stabilize	3/dentist
50%	422
60%	406
70%	355
80%	271
90%	153
Assumes interclass correlation coefficient (ICC) of 5%	

Assuming a 70% success rate, a 50% stabilization rate, an average of 3 patients per practitioners and an ICC of 5%, 600 patients are needed. To allow for a 10% attrition for success (end of treatment) and 20% attrition for stabilization (one year post treatment), this study would need to enroll 840 patients. This means we need to recruit about 210 orthodontists, who each need to recruit about 4 patients each.

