11.3 Final Analysis Plan

Analysis plan for Primary Objectives:

Primary objective #1 is to estimate the proportion of patients who are successfully treated. As described in section 3.2 (outcome measures), successful treatment is defined as occurring when patients have positive overlap at the end of treatment; this will be calculated with a 95% confidence interval.

Though not an explicit hypothesis, we expect those that are “successfully” closed will have had a smaller distance between the maxillary and mandibular incisor tips prior to treatment, i.e., at enrollment, than those not successfully closed. We will calculate the mean distance improved separately for those successfully treated and those not. It may be that those not successfully treated had more improvement than those who were successfully treated (if the former had a greater distance that needed to be corrected) and we want to capture this. Thus, as an additional but secondary measure of improvement, we will also calculate mean and median distance improved as descriptive measures.

Primary objective #2 is to estimate, among patients who are successfully treated, the proportion of patients whose treatment is stable. As described in section 3.2 (outcome measures), stability will be assessed one year after end of active treatment. The primary measure (strictest, most conservative classification) will be among patients who are determined to have been successfully treated at end of active treatment (having closed their AOB), what proportion of these have positive overlap at the one-year follow up time. This proportion will be estimated with a 95% confidence interval. Additional assessments of stability will include the proportion of all who had improvement in overbite (positive increases) during retention, no change in overbite during retention, and worsening of overbite (negative increases) during retention. We will calculate these mean and median changes as descriptive measures.

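### Stability is judged from overlap at the final visit alone, so a bite that reopened and was actively closed again before that visit would count as stable

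*Protocol*

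**What the plan says.** Section 3.2 defines the dichotomous stability outcome from the frontal photograph at follow-up: "A positive incisal overlap will be considered stable". Section 11.3 restricts it to patients closed at the end of active treatment and asks "what proportion of these have positive overlap at the one-year follow up time"; it adds that "This proportion will be estimated with a 95% confidence interval". Objective 3a in section 11.4.2 uses the same criterion, positive overbite one year after active treatment.

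Section 4 says participation does not influence the treatment that patients receive. Section 6.4 allows the final visit from 10 to 24 months after appliance removal.

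Section 7.1 has the practitioner record, at retainer checks, the open-bite status, changes of retainer or regimen, and "whether any additional adjunctive treatments have been completed since retention began". The Final Visit Form repeats these items. Patients also report whether the bite is closed. No section uses any of this to classify stability.

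**The concern.** The second primary estimate is meant to show whether a closed bite stays closed after active treatment ends. Under the stated rule, two different courses receive the same label: a correction that held, and a correction that failed and was then repeated. Usual care is unrestricted and follow-up lasts at least 10 months, so the second course is possible. The protocol's background (section 2.1) treats relapse as a real risk, and section 11.2 plans for stability as low as 50%.

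The misclassification has one direction. It can turn a failed correction into a stable one but never the reverse, and a larger sample does not reduce it. Objective 3a inherits the same label for its comparisons.

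**Working it through.** **1. The plan's own figures.** Inputs from section 11.2: "We want to estimate both success and stabilization rates with 10% precision"; "Assuming a 70% success rate, a 50% stabilization rate"; "an average of 3 patients per practitioners and an ICC of 5%, 600 patients are needed"; attrition of 10% to end of treatment and 20% to one year.

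- Design effect: 1 + (3 − 1) × 0.05 = 1.10.
- Patients at 50%: 1.96² × 0.25 / 0.05² × 1.10 = 422.6 (stated 422). The 60% to 90% rows give 405.7, 355.0, 270.4 and 152.1 (stated 406, 355, 271, 153).
- A half-width of 10 points would give 105.6 in the 50% row, so the stated precision is the full interval width and the half-width is 5 points.
- 422 / 0.70 = 603 (stated 600). 600 / (0.9 × 0.8) = 833 (stated 840).
- Closed patients evaluable for stability: 840 × 0.9 × 0.7 × 0.8 = 423. Half-width at 50%: 1.96 × √(1.10 × 0.25 / 423) = 0.050.

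The sample size reproduces and is not affected by this point.

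**2. Size of the bias.** Let S be the proportion of closed patients who show overlap at the final visit without renewed active treatment of a reopened bite. Let r be the share of the remaining 1 − S who were actively re-closed before that visit. The rule then reports

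observed = S + (1 − S) × r, so bias = (1 − S) × r.

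The documents do not give r; the values below are assumptions. S = 50% is the planning value, 65% is the lower end of the reported range in section 11.2, and 80% is illustrative. The half-width is 1.96 × √(1.10 × S(1 − S) / 422).

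| S | Half-width | r = 2% | r = 5% | r = 10% | r = 20% |
|---|---|---|---|---|---|
| 50% | 5.0 | +1.0 | +2.5 | +5.0 | +10.0 |
| 65% | 4.8 | +0.7 | +1.7 | +3.5 | +7.0 |
| 80% | 4.0 | +0.4 | +1.0 | +2.0 | +4.0 |

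(All entries in percentage points.)

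At S = 50%, r = 2%, 5% and 10% correspond to about 4, 11 and 21 of 422 patients (422 × 0.5 × r).

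**3. Effect on the interval.** With b the bias and se = √(1.10 × observed × (1 − observed) / 422), coverage of S is Φ(1.96 − b/se) − Φ(−1.96 − b/se). At S = 50% this is about 93%, 83% and 50% for r = 2%, 5% and 10%.

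**4. Would another planned analysis show it?** Section 11.3 also reports whether overbite improved, stayed the same or worsened during retention. The millimetric method in Appendix C uses photographs from the end of treatment and from the one-year visit. Both compare the same two time points as the primary measure, so a reopening that was repaired in between is invisible to them.

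**The case against.** **A different question.** The objective is stability determined at one year under usual care, and overlap at that visit measures that status directly. This stands in part: the overlap-only proportion is a legitimate quantity and should be kept. But it does not tell a correction that held from one that had to be repeated, and section 3.2 calls both stable.

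**A matter for the SAP.** Handling of intermediate events is often left there, and the SAP is not at hand. Here, however, the protocol itself fixes the primary classification in sections 3.2 and 11.3. The point is what that rule does, not a missing detail.

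**Unknown frequency.** This stands. A reader might infer that the stability proportion is in fact overstated, perhaps by 10 points. The documents do not support that. Only relapsed patients can be re-closed, so a 10-point bias needs r = 0.10 / (1 − S): 20% at S = 50%, 29% at 65% and 50% at 80%. The bite must also reopen, be noticed, be treated and show overlap, all before a visit planned at about one year. Nothing in the protocol says this is common.

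**Objective 3a.** A reader might infer that the modality or practice that re-treats most will look the most stable. That is possible if re-treatment differs between them, but no section shows that it does.

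**The conservative label.** Section 11.3 introduces its rule with "The primary measure (strictest, most conservative classification". One might read this as a false claim about re-treated patients. In context it contrasts the measure with the improved, unchanged and worsened summaries and says nothing about intermediate treatment.

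**Readiness of the data.** Section 7.1 lists adjunctive treatments but does not name re-treatment of the open bite, so the existing items may not capture it cleanly. A rule based on any further treatment would also count as failures patients who had top-up treatment without ever reopening. Both points stand and shape the fix.

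**Conclusion.** The point holds in a conditional form. By the stated definition, a closed patient who relapsed and was actively re-closed before the final visit is counted as stable. Any such patient raises the primary proportion, and no other planned summary would show it. At the planning value of 50% stability, a bias equal to the whole planned half-width requires one in ten relapsed patients to be re-closed. At 2% the bias is 1.0 point, and at 80% stability with r between 2% and 10% it is 0.4 to 2.0 points. These figures rest on assumed values of r and on the plan's ICC and cluster size. Distortion of objective 3a is possible but not shown. This is a weakness in the outcome definition that is cheap to remove. It is not a demonstrated numerical error, and the sample size of 840 is unaffected.

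**What to change.** In sections 3.2, 11.3 and 11.4.2 (3a), define stable as positive overlap at the final visit with no renewed active treatment directed at a reopened bite since appliance removal. Count patients who had such treatment as not stable. Derive this from the open-bite status, retainer or regimen change and adjunctive-treatment items on the Retainer Use and Final Visit forms, and clarify one item so that it names re-treatment of the open bite explicitly. The Final Visit Form matters most: section 6.3.2 gathers retainer-check information only during the first year, while the final visit may come as late as 24 months.

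State that top-up treatment with no recorded reopening does not count as relapse. Report the overlap-only proportion and the number re-treated, by modality, as supporting results.

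The cost is a few sentences and one form item. The stability figure may come out slightly less favourable, and an outcome read from photographs will depend in part on practitioner-reported re-treatment. The change concerns classification in the analysis only; it alters no care and no sample size.
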